
Statistical considerations
	
NUMBER OF SUBJECTS NEEDED
 
Dose escalation part
 
 
4 dose levels
 
A minimum of 3 patients and a maximum of 6 patients per dose level
 
Therefore, the maximum number of patients is estimated to be about 24 eligible and assessable patients. To account for patients not eligible/assessable, we anticipate accruing a maximum of 26 patients for the dose escalation part of the phase I trial.
 
 
Expansion cohort
 
 
Sample size is calculated based on the first stage of a 2-stage Gehan design assuming a 20% efficacy rate, 5% false positive rate and 10% precision (Gehan 1961).
 
14 eligible and assessable subjects are required.
 
If at least one non-progression (CR, PR or SD) is observed under treatment, the study drug association will be considered worthy of further testing in this indication.
 
Assuming, 10% are not eligible or cannot be assessed for the primary endpoint, 15 patients will be recruited in the expansion cohort.
 
 
STATISTICAL ANALYSIS
 
 
All analyses for the dose escalation part trial and the expansion cohorts will be descriptive; no p-values will be calculated. Data analyses will be provided by dose groups and for all study patients, combined wherever appropriate. For continuous variables, summary statistics will include number of patients, mean, median, standard deviation, standard error, minimum, and maximum. Categorical endpoints will be summarized using number of patients, frequency, percentages, and standard errors. Missing data will not be imputed.
 

	

• Objective response rate under treatment, best objective response rate under treatment, 6-month non-progression and 6-month objective response rates will be calculated using binomial estimates and reported with their 95% confidence interval (CI).

• Survival endpoints (PFS and OS) will be analyzed using the Kaplan-Meier method. The median survival rates will be reported with a 95% confidence interval. Median follow-up will be calculated using the reverse Kaplan-Meier method.

--	---

## 2 DEFINITION OF THE STUDY POPULATIONS

### 2.1 DÉFINITIONS

#### 2.1.1 DOSE ESCALATION PART

- Population assessable for DLT assessment :
  - Patients assessable for the DLT assessment must fulfill all the following criteria:
    - Completed the DLT assessment period
    - Received concomitantly at least seven consecutive days of Olaparib and radiotherapy treatment (any dose) at least once.
  - Unless they develop a DLT, the following patients will not be included in the population assessable for DLT :
    - Patients who did not receive radiotherapy
    - Patients who did not receive nor Olaparib;
    - Patients who did not complete the full DLT evaluation period and goes off-treatment for reasons other than toxicity;

***These patients will be replaced to reach the sample size requirement for dose escalation study.***

- Safety population: patients who received radiotherapy or olaparib, at least once, irrespective of the dose.

Criteria	eFORM variable	Control
DLT-assessable	EXA_RAD DLT_RA EXA_ONC DLT_ON TRT_OLA TH_20,...,TH_50 (4 variables therapy change) CH_20,...,CH_50 (4 variables reason of change)  TRT_RAD TH_2R,...,TH_10R (9 variables therapy change) CH_2R,...,CH_10R (9 variables reason of change)	ELI_DLT=0 If (DLT_RA =1 or DLT_ON=1) then ELI_DLT=1  Check if treatment stopped If ((TH_20 and ... and TH_50) in (0 -7) and (TH_2R and ... and TH_10R in (0 - 7)) then ELI_DLT=1  if treatment stopped check the reason (toxicity) and 7 consecutive days If ((TH_20 or ... or TH_50) in (2 3 4 5) or (TH_2R or ... or TH_10R in (2 3 4 5)) then {if (respectively ) ((CH_20 or ... or CH_50) in (1 2 3) or (CH_2R or ... or CH_10R in (1 2 3)) and (check start and end dates for seven consecutive days of olaparib and radiotherapy) then ELI_DLT=1 }
Safety Population	TRT_RAD CD_1R (cumulative dose d1) TRT_OLA DS_10 (total daily dose)	ELI_SAF=0 If (CD_1R > 0 or DS_10 >0 ) then ELI_SAF=1

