10.2. DEFINITION OF STUDY POPULATIONS

Dose escalation part

- Population assessable for DLT assessment :
 - Patients assessable for the DLT assessment must fulfill all the following criteria:
 - Completed the DLT assessment period
 - Received concomitantly at least seven consecutive days of Olaparib and radiotherapy treatment (any dose) at least once.
 - Unless they develop a DLT, the following patients will not be included in the population assessable for DLT :
 - Patients who did not receive radiotherapy
 - Patients who did not receive nor Olaparib;
 - Patients who did not complete the full DLT evaluation period and goes off-treatment for reasons other than toxicity;

These patients will be replaced to reach the sample size requirement for dose escalation study.

- Safety population: patients who received radiotherapy or olaparib, at least once, irrespective of the dose. .

Expansion cohort

- Eligible population: All patients included without major violation of eligibility criteria.
- Population eligible and assessable for the primary endpoint : patients who fulfill all criteria below:
 - Eligible patients
 - Received concomitantly at least seven consecutive days of Olaparib and radiotherapy treatment (any dose) at least once.
 - at least one disease measurement recorded not less than eight weeks after treatment onset.

The following patients will also be included in the population evaluable for efficacy; they will be considered as failures for the primary endpoint (i.e. progressive disease at 6 months) and not be replaced in the efficacy analysis:

- Eligible patients withdrawn due to drug-related toxicity without any tumor assessments after the start of study treatment.
- Eligible patients withdrawn due to significant clinical deterioration of unknown reason, hypersensitivity reactions, or unrelated AEs without any tumor assessments after the start of study treatment.
- ***Replacement of patients: patients who do not comply with the definition of the population "eligible and assessable for the primary endpoint" will be replaced to reach the sample size requirement for expansion cohort.***
- Safety population: patients who receive at least one administration of Olaparib, or radiotherapy treatment at least once.

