**CREATION OF A NEW INDICATOR VARIABLE**

Patients who completed the DLT assessment period and received concomitantly at least seven consecutive days of Olaparib and radiotherapy treatment or who developed DLT are included in the analysis (**ELI\_DLT = 1**)

Label: "DLT- assessable"

**ELI\_DLT=1** if the patient is assessable for DLT

**ELI\_DLT=0** otherwise

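### The SAP's ELI_DLT control does not implement the DLT-assessable population: it never tests completion of the DLT window, and on one reading of its codes it drops some completers

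*SAP*

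**What the plan says.** **The definition.** Protocol 10.2 and SAP 2.1.1 set two conditions for a patient without a DLT. The first is "Completed the DLT assessment period". The second is "Received concomitantly at least seven consecutive days of Olaparib and radiotherapy treatment (any dose) at least once". A patient is left out for going off treatment only when two things coincide: "Patients who did not complete the full DLT evaluation period and goes off-treatment for reasons other than toxicity". The block in SAP 2.1.1 that creates the indicator repeats the rule in one sentence, giving the value 1 to "Patients who completed the DLT assessment period and received concomitantly at least seven consecutive days of Olaparib and radiotherapy treatment or who developed DLT".

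**The control.** The SAP 2.1.1 table then gives the program for ELI_DLT, which starts at 0 and has three branches:

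- Branch 1 handles DLTs: "If (DLT_RA =1 or DLT_ON=1) then ELI_DLT=1".
- Branch 2 handles patients with no therapy change. It opens "If ((TH_20 and ... and TH_50) in (0 -7", applies the same test to the radiotherapy change codes, and sets the flag to 1.
- Branch 3 is headed "if treatment stopped check the reason (toxicity) and 7 consecutive days". It applies to change codes 2 to 5. It sets 1 only if the reason code is 1, 2 or 3 and a check of treatment dates shows the seven days.

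The variables listed are DLT flags, the dosing forms, therapy-change codes (TH) and reason codes (CH). The SAP does not say what the codes mean.

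**The concern.** The definition turns on window completion and seven days on both treatments. The control turns on whether treatment changed and why. These are different questions, so some patients will be classified one way by the text and the other way by the program.

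DLT incidence at each dose level is the primary endpoint of the escalation part (Protocol 9.1, SAP 3.2.1.1), and the SAP says that patients with the flag at 1 enter the analysis. Patients with a DLT are always kept, so every misclassification falls on DLT-free patients. An early leaver counted as assessable pulls the rate down. A completer set to 0 pushes it up. With only a few patients per level, one such patient is visible in the result.

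**Working it through.** **1. The plan's own size.** 4 levels × 6 patients = 24 assessable (SAP synopsis; the Protocol 10.1 rule of thumb gives the same). Accrual of up to 26 leaves 26 − 24 = 2 non-assessable patients, or 2/26 = 7.7%. The average is six per level, but the protocol guarantees only two at any level.

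**2. End of the window.** Radiotherapy starts on D8 and the last of 33 fractions falls on D52 (Protocol synopsis). Six weeks later is 52 + 42 = D94. This agrees with Protocol 3.4.1: 13.5 weeks × 7 = 94.5 days. The scheduled W14 visit is D92, two days earlier.

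**3. Text against program, for a patient without a DLT.**

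| Condition | Text | Branch 2 (no change) | Branch 3 (codes 2-5) |
|---|---|---|---|
| Window completed | required | not tested | not tested |
| Seven days on both treatments | required | not tested | tested |
| Reason for change | matters only if the window is incomplete | – | must be coded 1-3 |
| Date limit on the change | – | none | none |

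Example: a patient finishes unchanged treatment on D52 and is lost on D60. The text gives 0, because D60 is before D94. Branch 2 gives 1.

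**4. Count over all profiles.** The profiles cross:

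- DLT: yes or no (2);
- change and reason: none; code 2-5 with a toxicity or another reason; any other code with a toxicity or another reason (5);
- window completed: yes or no (2);
- seven days: yes or no (2).

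That makes 2 × 5 × 2 × 2 = 40. The text rule is 1 if DLT, or if completed and seven days.

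Reading `(0 -7)` as the two codes 0 and -7, the program disagrees with the text in 7 of 40.

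- Wrongly set to 1 (4): no change, window incomplete, with seven days; the same without seven days; no change, window completed, without seven days; code 2-5 for toxicity with seven days but an incomplete window.
- Wrongly set to 0 (3): completer with seven days and a code 2-5 change for a non-toxicity reason; completer with seven days and any other change code, whether the reason is toxicity or not, since no branch covers such codes.

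Reading it as the range 0 to 7, branch 2 admits everyone. The program then disagrees in 15 of 40, all wrongly set to 1, and branch 3 has no effect. The four wrong inclusions above are among the 15.

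One of the seven is debatable. A patient who stops early for toxicity short of a DLT fails the completion condition, yet the exclusion bullet names only other reasons for stopping.

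These are counts of logical profiles, not expected proportions of patients.

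**5. Effect on a level's rate (assumed counts).**

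- 2/6 = 33.3%. One early leaver added: 2/7 = 28.6%. One completer dropped: 2/5 = 40.0%.
- 1/6 = 16.7%. One added: 1/7 = 14.3%. One dropped: 1/5 = 20.0%.

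**The case against.** The definition itself is correct in Protocol 10.2 and twice in SAP 2.1.1. The Control column is partly working notes for a person: it mixes code with instructions to check dates or to see that fields are filled in. A statistician who programs from the definition would produce the right population. This stands in part. The fault lies in the control, and it bites only if the control is followed as written. But the control is the only specification of how the flag is derived, and nothing in it prompts a check of window completion.

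The loss of completers depends on codes that the SAP does not define. The control prints the list both as `(0 -7)` and as `(0 - 7)`, and codes 2-5 may cover stops only. This stands. That half of the point is conditional; the missing completion test is not.

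A reader might infer that the flag also decides who is replaced and who enters the final dose-toxicity model. The documents do not say so. Replacement is tied to the text definition. Protocol 10.3 does not link the model to ELI_DLT, and the SAP contains no such model. Under the TITE-CRM in Protocol 3.4.2, DLT-free patients with partial follow-up enter with partial weight. The patient lost at D60 would carry about 60/94.5 = 0.63, so early leavers are not counted there as fully observed. SAP 3.2.1.1 and Table 9.1 do not name the denominator either. The link to DLT incidence rests on the SAP's statement that flagged patients are included in the analysis.

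**Conclusion.** The concern holds in this form. The control for ELI_DLT contradicts its own definition under either reading of the code list, because window completion is never tested and the no-change branch tests nothing else. A DLT-free patient with unchanged treatment who is lost before about D94 is counted as assessable. On the two-code reading, and if codes 2-5 cover such changes, a completer with a change for a non-toxicity reason is set to 0. Because changes carry no date limit and olaparib may continue until progression, a change recorded after the window could have the same effect.

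Three stronger statements might be inferred and are not supported:

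- That the DLT denominators are wrong. They will be wrong whenever such a patient occurs and the control is followed. The plan does not show how many there will be, and the two errors pull in opposite directions.
- That either error carries a level across the 33% target. From 2/6 only the added patient does so (28.6%). Since 33.3% is already above 33%, 2/5 crosses nothing. After the first DLT, doses are in any case assigned from model estimates, not raw fractions.
- That a patient who never had radiotherapy is set to 1. This depends on what is stored in those fields, which the SAP does not say.

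The Monday-to-Friday schedule is a lesser matter. Seven consecutive days of radiotherapy cannot be read literally, but that wording comes from the protocol definition and needs only a workable rule.

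**What to change.** Replace the control with the rule that the SAP already states in words. Set ELI_DLT = 1 if either of these holds, and 0 otherwise:

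- a DLT occurred in the window; or
- the last safety assessment is at or after the last fraction + 42 days, with a stated visit tolerance, **and** there is at least one run of seven consecutive calendar days within radiotherapy with olaparib taken daily and the scheduled weekday fractions given.

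The tolerance must accept the scheduled W14 visit at D92. Otherwise a patient seen on schedule, with no later contact, fails by two days. The first condition should not require committee validation, because the documents differ on its timing: Protocol 12.1.2 has the committee consulted before the first escalation to a new level, the SAP synopsis at each DLT notification.

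Also:

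- remove the reason for a therapy change as a criterion for completers, and use it only to describe exclusions;
- state what the TH and CH codes mean;
- list separately any patient who left early for toxicity short of a DLT, since SAP 2.1.1 is unclear about them;
- name the DLT-assessable population as the denominator in SAP 3.2.1.1 and Table 9.1.

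Written this way, the rule agrees with the text in all 40 profiles. The cost is a small SAP and program edit using treatment and visit dates already collected. Study conduct does not change.

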**CREATION OF A NEW INDICATOR VARIABLE**

Patients who completed the DLT assessment period and received concomitantly at least seven consecutive days of Olaparib and radiotherapy treatment or who developed DLT are included in the analysis (**ELI\_DLT = 1**)

Label: "DLT- assessable"

**ELI\_DLT=1** if the patient is assessable for DLT

**ELI\_DLT=0** otherwise

**CREATION OF A NEW INDICATOR VARIABLE**

Patients who received radiotherapy or olaparib, at least once, irrespective of the dose. (**ELI\_SAF = 1**)

Label: "Safety Population"

**ELI\_SAF=1** if the patient is assessable for safety

**ELI\_SAF=0** otherwise

## 2.1.2 EXPANSION COHORT

- Eligible population: All patients included without major violation of eligibility criteria.
- Population eligible and assessable for the primary endpoint : patients who fulfill all criteria below:
  - Eligible patients
  - Received concomitantly at least seven consecutive days of Olaparib and radiotherapy treatment (any dose) at least once .
  - at least one disease measurement recorded not less than eight weeks after treatment onset.

The following patients will also be included in the population evaluable for efficacy; they will be considered as failures for the primary endpoint (i.e. progressive disease at 6 months) and not be replaced in the efficacy analysis:

- Eligible patients withdrawn due to drug-related toxicity without any tumor assessments after the start of study treatment.
- Eligible patients withdrawn due to significant clinical deterioration of unknown reason, hypersensitivity reactions, or unrelated AEs without any tumor assessments after the start of study treatment.
- ***Replacement of patients: patients who do not comply with the definition of the population "eligible and assessable for the primary endpoint" will be replaced to reach the sample size requirement for expansion cohort.***
- Safety population: patients who receive at least one administration of Olaparib, or radiotherapy treatment at least once.

## 2.2 ELIGIBILITY STATUS

### 2.2.1 INCLUSION CRITERIA

Criteria	eFORM variable	Control
1. Histology: patients with soft-tissue sarcoma histologically confirmed by central review (Pr [name] team), except if the diagnosis was already confirmed by the RRePS Network,	ELIGFORM C1I PRE2TRT HIS_REV	C1I=1 HIS_REV=1
2. Upper/Lower limb or trunk wall soft-tissue sarcoma,	ELIGFORM C2I PRE2TRT HIS_DIA	C2I=1 HIS_DIA in ( 1 2 3)
3. Age $\geq$ 18 years,	ELIGFORM C3I INCFORM DT_CONS DT_BIRTH	C3I=1 (DT_CONS-DT_BIRTH) $\geq$ 18
4. Locally advanced or locally recurrent inoperable tumor, outside any previously irradiated field (inoperable status must be assessed by staff including a surgeon specialized in sarcoma),	ELIGFORM C4I PRE2TRT LOC_ADV LOC_INO	C4I=1 (LOC_ADV =1 or LOC_INO=1)
5. Eastern Cooperative Oncology Group (ECOG), performance status $\leq$ 2,	ELIGFORM C5I PRE1TRT ECOG_PTR	C5I=1 ECOG_PTR in (0 1 2)
6. Life expectancy $\geq$ 6 months,	ELIGFORM C6I	C6I=1 Investigator decision
7. At least one lesion, not previously irradiated, that can be accurately measured at baseline as $\geq$ 10 mm in the longest diameter (except lymph nodes which must have short axis $\geq$ 15 mm) with magnetic resonance imaging (MRI) and which is suitable for accurate repeated measurements,	ELIGFORM C7I TUM_ASS NUM_LM MEA1L,...,MEA5L (5 variables)	C7I=1 NUM_LM $\geq$ 1 and Depending on NUM_LM value (MEA1L and ... and MEA5L) $\geq$ 10 + Investigator decision regarding irradiation and suitability for repeated measurements
8. Adequate hematological, renal, metabolic and hepatic	ELIGFORM C8I PRE3TRT	C8I=1 HEMO $\geq$ 9 NEUT $\geq$ 1.5 x 10 


function:
 
 
- Haemoglobin <math>\geq 9</math> g/dL and no blood transfusions in the 14 days prior to study entry
 
- Absolute neutrophil count (ANC) <math>\geq 1.5 \times 10^9/L</math>
 
- Platelets <math>\geq 100 \times 10^9/L</math>
 
- Total bilirubin <math>\leq 1.5 \times</math> upper limit of normality (ULN),
 
- Alanine aminotransferase (ALAT) or aspartate aminotransferase (ASAT) <math>\leq 2.5 \times</math> ULN,
 
- Serum creatinine <math>\leq 150 \mu\text{mol/L}</math> or creatinine clearance <math>\geq 50 \text{ mL/min}</math> (according to local institution) in case of serum creatinine <math>> 150 \mu\text{mol/L}</math>,
 
- TP, INR <math>\leq 1.5 \times</math> ULN
 
	
HEMO NEUT PLAT BIL_TOT ALT AST CREA CCLE TP INR
	
PLAT <math>\geq 100 \times 10^9</math> CREA <math>\leq 150</math> or CCLE <math>\geq 50</math>

9. Women of childbearing potential must have a negative serum pregnancy test within 28 days of study treatment, confirmed prior to treatment on day 1. Female patients of child bearing potential and their partners, who are sexually active, must agree to the use of two highly effective forms of contraception in combination throughout the period of taking study treatment and for at least 1 month after last dose of study drug. Males patients, who are sexually active, must agree to the use of two highly effective forms of contraception in combination throughout the period of taking study treatment and for at least 3 month after last dose of study drug. Acceptable birth control methods are described in appendix 10. Subjects of non-childbearing
	
ELIGFORM C9I INCFORM FEM_STA DT_PREG RES_PREG FEM_REA (non childbearing potential) REA_OTH TRT_OLA DT_S10 (D1 olaparib) PRE3TRT CONT_PTR (contraception) SPE_CONT
	
C9I=1
 
(FEM_STA =1 and RES_PREG=0 and (DT_S10-DT_PREG <math>\leq 28</math>))
 
(CONT_PTR =1 and check SPE_CONT)
 
If (FEM_STA =0 ) then Check FEM_REA and REA_OTH

potential are those who have: 
 
• Amenorrheic for 1 year or more following cessation of exogenous hormonal treatments,
 
• LH and FSH levels in the post menopausal range for women under 50,
 
• radiation-induced oophorectomy with last menses >1 year ago,
 
• chemotherapy-induced menopause with >1 year interval since last menses,
 
• or surgical sterilisation (bilateral oophorectomy or hysterectomy).
 
		
10. Patient is willing and able to comply with the protocol for the duration of the study including undergoing treatment and scheduled visits and examinations including follow up,	ELIGFORM C10I	C10I=1 Investigator decision
11. Voluntary signed and dated written informed consent prior to any specific procedure,	ELIGFORM C1I INCFORM DT_CONS	C11I=1 DT_CONS filled in
12. Patients with a French social security in compliance with the Law relating to biomedical research (Article L.1121-11 of French Public Health Code).	ELIGFORM C12I	C12I=1 Investigator decision

## 2.2.2 NON-INCLUSION CRITERIA

Criteria	eFORM variable	Control
1. Any previous treatment with a PARP inhibitor, including Olaparib,	ELIGFORM C1NI PRE2TRT NAM_TRT (chemo treatment)	C1NI=0 Check NAM_TRT Investigator decision
2. Patients unable to swallow orally administered medication and patients with	ELIGFORM C2NI PRE1TRT	C2NI=0 Check if (PAT1_PTR and ... and PAT10PTR NE 3)

gastrointestinal disorders likely to interfere with absorption of the study medication,	PAT1_PTR,...,PAT10PTR (10 variables)	Investigator decision
3. Immunocompromised patients, e.g., patients who are known to be serologically positive for human immunodeficiency virus (HIV) and are receiving antiviral therapy,	ELIGFORM C3NI PRE3TRT HIV	C3NI=0 HIV=0 Investigator decision
4. Patients with known active hepatic disease (i.e., Hepatitis B or C) due to risk of transmitting the infection through blood or other body fluids,	ELIGFORM C4NI PRE3TRT HEP_B HEP_C	C4NI=0 HEP_B=0 HEP_C=0
5. Patients considered a poor medical risk due to a serious, uncontrolled medical disorder, non-malignant systemic disease or active, uncontrolled infection. Examples include, but are not limited to, uncontrolled ventricular arrhythmia, recent (within 3 months) myocardial infarction, unstable spinal cord compression (untreated and unstable for at least 28 days prior to study entry), superior vena cava syndrome, extensive bilateral lung disease on HRCT scan or any psychiatric disorder that prohibits obtaining informed consent,	ELIGFORM C5NI PRE1TRT PAT1_PTR,...,PAT10PTR (10 variables)  Pathology codes : 1=Cardiovascular 9= psychiatric 15= Other	C5NI=0 Check if (PAT1_PTR and ... and PAT10PTR not in (1 9 15) ) + Investigator decision
6. Patients with uncontrolled seizures,	ELIGFORM C6NI PRE1TRT PAT1_PTR,...,PAT10PTR (10 variables) Pathology codes : 8=Neurological	C6NI=0  Check if (PAT1_PTR and ... and PAT10PTR not in (8) )
7. Men or women of childbearing potential who are not using an effective method of contraception as previously describes; women who are pregnant or breast feeding,	ELIGFORM C7NI INCFORM FEM_STA DT_PREG RES_PREG	C7NI=0 (CONT_PTR =1 and check SPE_CONT) (FEM_STA =1 and RES_PREG=0 )

	FEM_REA (non-childbearing potential) REA_OTH TRT_OLA DT_S10 (D1 Olaparib) PRE3TRT CONT_PTR (contraception) SPE_CONT	
8. No prior or concurrent malignant disease diagnosed or treated in the last 2 years, except for adequately treated in situ carcinoma of the cervix, basal or squamous skin cell carcinoma, or in situ transitional bladder cell carcinoma,	ELIGFORM C8NI	C8NI=0  Investigator decision
9. Patients receiving any systemic chemotherapy, radiotherapy (except for palliative reasons), within 2 weeks from the last dose prior to study treatment (or a longer period depending on the defined characteristics of the agents used),	ELIGFORM C9NI PRE2TRT DT_LSEQ DT_ECHE TRT_OLA DT_S10 (D1 Olaparib)	C9NI=0  (DT_S10-DT_LSEQ >2) and (DT_S10-DT_ECHE >2)  + Investigator decision
10. Concomitant use of known CYP3A4 inhibitors such as ketokonazole, itraconazole, ritonavir, indinavir, saquinavir, telithromycin, clarithromycin and nelfinavir,	ELIGFORM C10NI	C10NI=0  Investigator decision
11. Resting ECG with QTc > 470msec on 2 or more time points within a 24 hour period or family history of long QT syndrome,	ELIGFORM C11NI PRE1TRT ECG_PTR QT_PTR	C11NI=0 (ECG_PTR=1 and QT_PTR < 470)
12. Blood transfusions within 14 days prior to study start,	ELIGFORM C12NI	C12NI=0 Investigator decision
13. Patients with myelodysplastic syndrome/acute myeloid leukaemia,	ELIGFORM C13NI PRE1TRT PAT1_PTR,...,PAT10PTR (10 variables) Pathology codes : 7 = Hemato-immunological	C13NI=0  Check if (PAT1_PTR and ... and PAT10PTR not in (7) )
14. Major surgery within 14 days of starting study treatment and patients must	ELIGFORM C14NI PRE2TRT	C14NI=0 (DT_S10-DT_SURG >14) and (DT_S10-DT_SURM >14)

have recovered from any effects of any major surgery,	DT_SURG DT_SURM	+ Investigator decision
15. Participation to a study involving a medical or therapeutic intervention in the last 30 days,	ELIGFORM C15NI	C15NI=0 Investigator decision
16. Patient unable to follow and comply with the study procedures because of any geographical, familial, social or psychological reasons,	ELIGFORM C16NI	C16NI=0  Investigator decision
17. Previous enrolment in the present study,	ELIGFORM C17NI	C17NI=0 Investigator decision
18. Patients with a known hypersensitivity to olaparib or any of the excipients of the product.	ELIGFORM C18NI	C18NI=0 Investigator decision

Criteria	eFORM variable	Control
Eligible Population	ELIGIBILITY FORM C1I C2I C3I C4I C5I C6I C7I C8I C9I C10I C11I C12I C1NI C2NI C3NI C4NI C5NI C6NI C7NI C8NI C9NI C10NI C11NI C12NI C13NI C14NI C15NI C16NI C17NI C18NI	ELI=1 If (C1I=0 OR C2I=0 OR C3I=0 OR C4I=0 OR C5I=0 OR C6I=0 OR C7I=0 OR C8I=0 OR C9I=0 OR C10I=0 OR C11I=0 OR C12I=0 OR C1NI=1 OR C2NI=1 OR C3NI=1 OR C4NI=1 OR C5NI=1 OR C6NI=1 OR C7NI=1 OR C8NI=1 OR C9NI=1 OR C10NI=1 OR C11NI=1 OR C12NI=1 OR C13NI=1 OR C14NI=1 OR C15NI OR C16NI=1 OR C17NI=1 OR C18NI=1) then ELI=0

